7.2 Exclusion Criteria

- 7.2.1 Baseline peripheral neuropathy from any cause**
- 7.2.2 Planned oxaliplatin with capecitabine**
- 7.2.3 Planned initial dose of oxaliplatin $<100\%$ of the standard regimen-specified dose**
For most regimens, this would be 85mg/m² IV dosed every 14 days.
- 7.2.4 Receipt of acupuncture treatment in the prior 3 months**
- 7.2.5 Use of concomitant duloxetine for minimization of neuropathy.**
- 7.2.6 Psychiatric illness/social situations that would limit compliance with study requirements.**

[figure not shown]
8.0 SUBJECT REGISTRATION

Subjects will be registered by the Fred Hutch/UW Study Coordinator and their data entered into OnCore CTMS. A complete, signed, study consent and HIPAA consent are required for registration.

9.0 TREATMENT PLAN

56 patients will be randomized 1:1 to the intervention arm (n=28) of standard oral cryotherapy with acupuncture or the control arm (n=28) of oral cryotherapy alone. All patients will receive standard-of-care supportive care medications (analgesics, antiemetics, etc.) at the discretion of their treating physician.

9.1 Treatment Plan Overview

9.2 Acupuncture and Acupressure Intervention

The intervention group will receive acupuncture during chemotherapy infusion (day 1) and 5-FU pump disconnect (day 3) of each biweekly chemotherapy infusion x6 cycles (*i.e.* 12 acupuncture treatments over 12 weeks). Acupuncture treatments will be specifically targeted to prevent, treat, or mitigate neuropathy symptoms, pain, fatigue, nausea and anxiety. Patients will receive 30-minute acupuncture treatments in the seated or supine position. Standard acupoint techniques for point location²² will be utilized and Clean Needle Technique²³ will be followed using 32-40-gauge x 30-40mm Seirin acupuncture needles.

On day 1 the acupuncture points will be needled bilaterally at: ST36, SP6, LI10, GB40, P6, auricular shen men, and on the midline at Yin Tang (EX-HN3) and GV20. On day 3 the acupuncture points will be needled bilaterally at: LI4, LR3, ST36, SP6, LI10, GB40, P6, auricular shen men, and on the midline at Yin Tang (EX-HN3) and GV20. For patients unable to tolerate peripheral cryotherapy, the day 3 acupuncture protocol will be administered on day 1.

After the initial acupuncture treatment, the study acupuncturist will instruct the patient on how to locate and self-administer acupressure for key acupoints: bilateral LI4 (for pain, oral dysesthesia), bilateral P6 (nausea), and midline GV20 (fatigue). These acupoints are based on previously published studies,¹²⁻¹⁵ Traditional Chinese Medicine (TCM) theory,²² and current understanding of innervation and neuromodulation of acupoints.¹³ Auricular shen men points (anxiety) will be stimulated with vaccaria seeds applied by the acupuncturists on day 3 and removed after 4 days (day 7 of the cycle). Patients will be taught to self-administer an 11-minute acupressure regimen daily by stimulating each acupoint in a circular motion for 2 minutes on each bilateral points of LI4 and P6, 2 minutes on midline GV20, and to gently press the ear seeds on shen men for 30 seconds three times per day. The acupuncturists will provide additional teaching during the acupressure training on Cycle 1 Day 1 instructing the patients to utilize auricular Shen Men point during cryotherapy to help mitigate possible unpleasant effects of cryotherapy including: headache, toothache, and/or cold aversion/pain.

If a patient misses an acupuncture session, it will not be made up. If a patient misses both sessions from 1 of chemotherapy, they will be removed from the study. Handouts describing acupuncture and acupressure will be provided to participants (Appendix L).

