6.1.2 Secondary Objectives

- 1: To estimate the incidence of grade 2 or higher CIPN following 3 months of acupuncture/acupressure treatment plus oral cryotherapy compared to oral cryotherapy alone.
- 2: To evaluate the severity of CIPN in GI cancer patients receiving oxaliplatin-based chemotherapy following 3 months of acupuncture/acupressure treatment plus oral cryotherapy compared to oral cryotherapy alone using objective measurement tools.
- 3: To assess the feasibility of delivering acupuncture during biweekly chemotherapy infusion and the feasibility of patient self-administered acupressure between infusions.
- 4: To evaluate the effect of oral cryotherapy with acupuncture/acupressure vs. oral cryotherapy alone in reducing pain, fatigue, nausea, oral dysesthesia, and anxiety in GI cancer patients receiving oxaliplatin-based chemotherapy.

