6.3.2 Secondary Endpoints

Incidence of grade 2 or higher CIPN as measured by CTCAE version 5.

Severity of CIPN as measured by a Neuropen and tuning fork.

Proportion of patients assigned to the intervention arm who complete 60% of acupuncture treatments.

Incidence of pain, fatigue, nausea, oral dysesthesia, and anxiety as measured by the NCI PRO-CTCAE, BPI, and CTCAE version 5.

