16.0 STATISTICAL CONSIDERATIONS

16.1 Study Design

This is a randomized, controlled feasibility trial of acupuncture treatment delivered during planned chemotherapy infusion and 5-FU pump disconnect appointments, and self-administered acupressure plus oral cryotherapy compared to oral cryotherapy alone for prevention of CIPN.

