16.5 Statistical Analysis

Severity of CIPN (EORTC-CIPN-20 score) at 3 months will be summarized for each treatment arm, and treatment comparisons made via linear regression model with adjustment for baseline severity level. Adherence to acupuncture treatment among patients in the intervention arm will be described as a proportion with 95% confidence interval. Reasons for treatment non-adherence and delivered dose intensity of chemotherapy will be noted. Incidences of CIPN (grade 2 or higher), pain, fatigue,

nausea, and anxiety will be compared between treatment arms using Chi-squared or Fisher's exact tests as appropriate. As this is a pilot study, we will not have adequate power to adjust for covariates such as age, gender, and existing comorbidities.

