20.10 APPENDIX J: Acupressure Diary

| Acupressure Weekly Diary | |
|--|---|
| Complete the diary on the back each day and bring it to your Day 1 acupuncture sessions | |
| Mark each time you complete your self-acupressure sessions | |
| A session consists of stimulating all four acupoints for a total of seven areas | |
| Use the Comments area for questions or were not able to complete the full session | |
| Brief Summary of Acupoint Locations and Instructions | |
| Use your thumb or fingertips to apply gentle, firm pressure to each point | |
| Press and hold or make circular motions on the acupoint, do not press so hard that it hurts | |
| These acupressure points help prevent or decrease pain, nausea, fatigue and anxiety | |
| Apply acupressure to each of these points on your left and right hands for two minutes | |
|  |  |
| Apply acupressure to this point on the center of your head | Apply acupressure to the point on each ear for 30 seconds |
|  |  |

| Study ID: | | | | Date Cycle Day 1 | | |
|-----------------------|------------|------------|------------|----------------------------------|---|---|
| Cycle # circle one | 1 | 2 | 3 | 4 | 5 | 6 |
| | Session #1 | Session #2 | Session #3 | Comments | | |
| Day 1 | | | | Acupuncture in clinic | | |
| Day 2 | | | | | | |
| Day 3 | | | | Acupuncture in clinic | | |
| Day 4 | | | | | | |
| Day 5 | | | | | | |
| Day 6 | | | | | | |
| Day 7 | | | | | | |
| Day 8 | | | | Remove Vaccaria Ear Seeds | | |
| Day 9 | | | | | | |
| Day 10 | | | | | | |
| Day 11 | | | | | | |
| Day 12 | | | | | | |
| Day 13 | | | | | | |
| Day 14 | | | | | | |

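### Does the self-acupressure half of secondary objective 3 need its own endpoint and a fixed session count in the plan?

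*Combined protocol and SAP*

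**What the plan says.** Objective 3 in protocol 6.1.2 has two halves, and the second is "the feasibility of patient self-administered acupressure between infusions". Section 16.1 describes the tested package as acupuncture "and self-administered acupressure plus oral cryotherapy compared to oral cryotherapy alone for prevention of CIPN".

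The only feasibility endpoint, in 6.3.2 and again in 16.2.2, is "Proportion of patients assigned to the intervention arm who complete 60% of acupuncture treatments". Section 16.5 follows it: "Adherence to acupuncture treatment among patients in the intervention arm will be described as a proportion with 95% confidence interval". The next sentence adds: "Reasons for treatment non-adherence and delivered dose intensity of chemotherapy will be noted".

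On the regimen, 9.2 says: "Patients will be taught to self-administer an 11-minute acupressure regimen daily by stimulating each acupoint in a circular motion for 2 minutes". The same sentence ends "and to gently press the ear seeds on shen men for 30 seconds three times per day". The diary in Appendix J defines its unit: "A session consists of stimulating all four acupoints for a total of seven areas". It prints columns for sessions 1, 2 and 3 on each of 14 days, and asks for a mark for every session completed.

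Section 10.1 and footnote 4 of the study calendar (Appendix B) trigger retraining at cycle 2 when a patient has done less than half of what was prescribed. The calendar also schedules diary review on day 1 of every later cycle and at end of treatment.

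**The concern.** A feasibility trial that states a feasibility aim would normally name the measure that answers it. Here the acupuncture half has a threshold and a confidence interval, and the acupressure half has neither. Noting reasons for non-adherence does not measure how much acupressure was done.

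A percentage of prescribed sessions also needs a denominator, and 9.2 and the diary seem to give different ones. If the choice is left until the data are in, the reported adherence could differ threefold depending on which document is followed. The 50% retraining rule has the same ambiguity.

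**Working it through.** **What the 11 minutes covers.** Inputs are from 9.2: LI4 and P6 on both sides at 2 minutes each, GV20 at 2 minutes, and ear points at 30 seconds each.

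- One pass: 2×2 + 2×2 + 2 + 2×0.5 = 11 minutes, over 2 + 2 + 1 + 2 = 7 areas. This reproduces the stated length and matches the diary's definition of one session.
- Each ear pressed three times: 10 + 2×0.5×3 = 13 minutes.
- Whole regimen three times: 3×11 = 33 minutes.

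One 11-minute regimen is therefore one diary session.

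**Denominators for a 14-day cycle.**

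| Reading | Per cycle | Six cycles | One session every day scores | Retrain if below |
|---|---|---|---|---|
| Once daily (9.2 'daily') | 14×1 = 14 | 84 | 14/14 = 100% | 7 |
| Three a day (diary columns) | 14×3 = 42 | 252 | 14/42 = 33% | 21 |

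A cycle 1 total of 7 to 20 sessions is classified oppositely by the two readings.

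These are not the only candidates. If the two in-clinic days are left out (an assumption), the counts are 12 and 36, the cuts are 6 and 18, and the discordant range is 6 to 17. Ear seeds are in place for only part of each cycle, and calendar footnote 6 lets procedures move with delayed chemotherapy, so a cycle need not last 14 days. No single fixed count per cycle would suit every patient.

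**How firm is the 42?** It comes from counting blank cells. No sentence in Appendix J requires three sessions. Section 9.2 does state a frequency, and in its sentence the three-times phrase directly follows the ear-seed instruction. As a matter of grammar that reads as one full regimen a day with the ear seeds pressed three times. I take no view on which frequency is right.

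**What the analyst has.** The numerator is recorded by day and by session. Mean sessions per day on study, and the share of days with at least one session, can both be computed without choosing between 14 and 42, and both cope with delayed cycles.

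**Precision.** With 28 patients in Arm A, exact (Clopper-Pearson) 95% intervals for a proportion reaching some cut would be 31% to 69% for 14/28 and 55% to 89% for 21/28.

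**What depends on the diary.**

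- Primary analysis (16.5): regression of the 3-month CIPN-20 score on arm and baseline. No diary input.
- Sample size (16.3): 50/0.9 = 55.6, so 56. No diary input.
- Acupuncture endpoint: 60% of 12 is 7.2, so at least 8 sessions attended. No diary input.
- Retraining: by 10.1 and footnote 4, one decision per Arm A patient, at cycle 2.

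**The case for a change.** The best case for a change is that feasibility is what a pilot should answer, that the plan gives acupuncture a formal measure, and that one descriptive line on acupressure would cost almost nothing. Fixing the summary beforehand would also prevent a later choice between figures that differ threefold. Nor does the once-daily reading of 9.2 fully explain the diary. By the diary's own definition an ear-seed press alone is not a session, so three session columns do not fit a once-daily regimen.

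Much of this stands. No acupressure endpoint is listed, and the form and the protocol text do not match. A mark in column 2 or 3 could mean a full session or only an ear press, and that would have to be stated when results are reported.

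It falls short of requiring a change because nothing inferential depends on the figure. Even the acupuncture measure has no target proportion; it is simply described with an interval. An acupressure summary would be of the same kind, from data already collected and reviewed. A responder cut would be a matter of preference, and a fixed count per cycle would fail when cycles are delayed. The mismatch between the day on which ear seeds come off in 9.2 and Appendix L (day 7) and in the diary (the day 8 row) is a clerical slip with no bearing on adherence counts.

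**Conclusion.** The concern is factually correct but calls for no change to the statistical plan. The missing acupressure measure is a gap that analysts would fill sensibly with a descriptive summary of the diaries. The 14-or-42 question sets a stated daily frequency against the layout of a form. Its operational reach is one retraining decision per Arm A patient at cycle 2, for cycle 1 totals of 7 to 20 sessions on a full 14-day grid.

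The investigators must reconcile section 9.2 with Appendix J on session frequency, and the seed-removal day across 9.2, Appendix J and Appendix L. Those are wording corrections for them to settle.

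The conclusion rests on three assumptions: diaries are kept and entered by day, any acupressure result is reported as descriptive, and the report states the denominator it uses. If acupressure adherence were to drive a decision on a later trial or a dose-response analysis, the count would need to be fixed first. The plan proposes neither.

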9.9 End of Treatment (EOT) Visit Schedule and Procedures

The EOT visits for all subjects who discontinue from the study should ideally occur 14 days after day 1 of the prior cycle of chemotherapy (which would be 11 days from the last acupuncture treatment). The EOT visit is permitted in the range of 7-30 days after the last use of (Arm A) acupuncture treatment or (Arm B) cryotherapy use but must occur prior to beginning another treatment or receiving another dose of chemotherapy. Procedures to be performed during the EOT Visit include:

- Physical Exam
- Administration of the final QOL measures
- Vital Signs
- Performance Status
- AE Assessment
- Concomitant Medication

As per 6.7. patients who are on the waitlist control arm and choose to use their acupuncture coupons will have the optional EOT visit for uniform data collection, but will also have limited data collected at the time of each acupuncture session to note any toxicities or major symptoms at the time of those visit.

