11.0 SUBJECT DISCONTINUATION OF ACTIVE TREATMENT

Subjects may be removed from this study at any time at their discretion. Subjects may also be removed from this protocol if they develop any untoward side effects from the study procedures (acupuncture).

If a subject withdraws consent to participate in the study or aspects of the study, attempts should be made to obtain permission to record survival data up to the protocol-described end of the subject follow-up period. Documentation in the medical record should state that the subject is withdrawing from the study and what, if any, selected data the subject will permit the investigator to obtain.

If a subject withdraws consent and has received less than 1 cycle of chemotherapy with associated study-specified treatment (including any planned acupuncture sessions for that cycle), an additional patient will be recruited. Patients who receive less than 1 cycle of chemotherapy will not be followed.

An explanation for discontinuing treatment is recorded for each subject discontinuing treatment on the appropriate CRF/eCRF. The PI must be notified immediately if a subject discontinues treatment. All subjects, irrespective of treatment status, will continue to be followed for survival. Treatment in this study must be discontinued for any of the following reasons:

- at Investigator's discretion;
- at the subject's request;
- if the subject enrolls in a trial of another investigational agent which does not permit concurrent treatment;
- if the patient misses both acupuncture sessions from cycle 1 of chemotherapy;
- Grade 4 or life-threatening toxicity (See Section 13, Adverse Events) attributable to the study intervention;
- change in chemotherapy regimen which no longer includes oxaliplatin;
- pregnancy.

If a patient discontinues use of oxaliplatin, he/she may continue to receive acupuncture either weekly or as protocolized (twice weekly every other week) until the completion of 3 months duration of acupuncture treatment.

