16.3 Sample Size and Power

This is a pilot study in which preliminary estimates of CIPN severity will be obtained under two treatment conditions. Complete data from 50 patients will provide 80% power to detect a difference in EORTC-CIPN-20 of 0.7 standard deviation units, based on a t-test with 1-sided alpha=0.05. To account for 10% potential loss to follow-up, we will enroll 56 patients, 28 on the intervention arm of acupuncture/acupressure and 28 on the standard-of-care arm. Patients who enroll, but are not treated, or received less than one cycle of chemotherapy with associated study-specific treatment (including any planned acupuncture sessions for that cycle), may be replaced as detailed in section 11.0.

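### Section 9.2 removes from the study an Arm A patient who misses both cycle-1 acupuncture sessions, while 11.0 only stops treatment; if 9.2 is followed, the 3-month CIPN-20 score is lost under a rule that can act in one arm only.

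*Combined protocol and SAP*

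**What the plan says.** Section 9.2, on the intervention, says that missed sessions are not made up and then: "If a patient misses both sessions from 1 of chemotherapy, they will be removed from the study". A word is missing before the 1; section 11.0 supplies it.

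Section 11.0, on discontinuation of active treatment, introduces a list with "Treatment in this study must be discontinued for any of the following reasons" and includes in it "if the patient misses both acupuncture sessions from cycle 1 of chemotherapy". It also says "All subjects, irrespective of treatment status, will continue to be followed for survival", and separately that patients given less than one cycle of chemotherapy are not followed. It provides for an extra recruit under this condition: "If a subject withdraws consent and has received less than 1 cycle of chemotherapy with associated study-specified treatment".

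Section 16.3 says that patients who enrol but are not treated, or who "received less than one cycle of chemotherapy with associated study-specific treatment (including any planned acupuncture sessions for that cycle), may be replaced", and refers to 11.0 for the details.

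Section 9.9 says that the end-of-treatment (EOT) visit for subjects who discontinue from the study "should ideally occur 14 days after day 1 of the prior cycle of chemotherapy". The permitted range for Arm A is "7-30 days after the last use of (Arm A) acupuncture treatment". The final quality-of-life measures are taken at that visit. Section 9.7 ends follow-up once the EOT questionnaires are done, apart from waitlist acupuncture visits.

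Sections 10.2 and 10.3 schedule assessments at baseline, 6 weeks and 12 weeks. The calendar in Appendix B has no 12-week column apart from End of Tx. Section 16.5 compares CIPN-20 at 3 months between arms by linear regression adjusted for baseline, and names no analysis set.

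**The concern.** Stopping an intervention and leaving a study have different consequences for the data. A patient who stops can still give the outcome; a patient who is removed normally does not. The plan attaches both consequences to one event and does not say which governs.

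The event happens after randomisation and depends on attending sessions that only Arm A is offered. An Arm B patient with the same circumstances or motivation has nothing to miss and stays in. If the removed patients would have had different neuropathy at three months from the rest of Arm A, the retained Arm A patients are no longer comparable with Arm B. This touches the primary endpoint analysis, on which the trial is sized. A 12-week score that was not collected cannot be recovered later.

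**Working it through.** **1. Which arm can trigger the rule.** The synopsis says the control arm gets no acupuncture in the 3-month period, and footnote 3 of the calendar restricts the cycle 1-6 sessions to Arm A. Only Arm A can trigger it.

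**2. What is collected if 9.2 is followed.** Cycles last 14 days.
- Six cycles completed: day 1 of cycle 6 is 5 × 14 = 70 days after the start, and the EOT visit falls at 70 + 14 = 84 days, which is week 12.
- Removed after cycle 1: the EOT visit falls at 0 + 14 = 14 days, about week 2.

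Apart from baseline, that week-2 visit is the only planned score, and 9.7 then closes follow-up. The permitted Arm A window cannot be computed for a patient who had no acupuncture, although the ideal date, which counts from chemotherapy, still can.

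**3. What is collected if 11.0 is followed.** The 12-week assessments in 10.2 and 10.3 could still be due. But 11.0 states continued follow-up only for survival, it also says that patients with less than one cycle are not followed (in either arm), and the calendar times the last assessment by the EOT visit. The text does not settle it.

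**4. Replacement.** Section 11.0 ties replacement to withdrawal of consent. Section 16.3 can be read to allow it when the cycle's planned acupuncture was not received.

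**5. The plan's own sample size.** Inputs from 16.3: 25 per arm, 0.7 SD, one-sided alpha 0.05. Power is 79.7% by the normal approximation and 78.7% by the noncentral t, against 80% stated. Enrolment: 50 / 0.9 = 55.6, rounded up to 56. Both reproduce.

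**6. Size of a possible bias.** The documents give neither a removal rate nor a score difference, so both are assumed. The sizing t-test stands in for the baseline-adjusted regression.
- Bias in SD = share removed × difference between removed and retained Arm A patients.
- Type I error = P(T > t(0.95; 48)), where T is noncentral t with 48 degrees of freedom and noncentrality bias × √(25 × 25 / 50) = bias × √12.5.

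For one of 28 removed:

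| Assumed 3-month difference | Bias (SD) | One-sided type I error |
|---|---|---|
| 1.0 SD worse | 0.036 | 6.4% |
| 0.7 SD worse | 0.025 | 6.0% |
| 0.5 SD worse | 0.018 | 5.7% |
| none | 0 | 5.0% |
| 0.5 SD better | 0.018, reversed | 4.4% |
| 0.7 SD better | 0.025, reversed | 4.2% |
| 1.0 SD better | 0.036, reversed | 3.8% |

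Using 27 against 28 patients instead of 25 per arm gives 5.7% and 6.5% for 0.5 and 1.0 SD worse, so the choice of n hardly matters.

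**The case against.** The strongest reply is that the rule will seldom apply. Acupuncture is given at the chemotherapy infusion and at the pump disconnect, when the patient is attending anyway. Sections 9.8 and the calendar move sessions with any chemotherapy delay, and missing one session is not enough. This stands, and it limits the size of the point.

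Where cycle 1 of chemotherapy itself is not completed, the 11.0 sentence that ends following applies to both arms, so not every early loss is confined to Arm A. That also stands, and it means the sentence has to be part of the repair.

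Part of the conflict may be loose drafting: 11.0 is headed as discontinuation of treatment but opens by speaking of removal from the study. That may explain the conflict but does not tell staff what to collect.

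A reader might infer that the error rate could more than double. With 15% of Arm A removed and those patients 1.0 SD worse, the formula gives 13.1%. The documents do not support that scenario. It means 0.15 × 28 = 4.2 patients lost to this rule alone, while 16.3 allows 10% loss from all causes, which is 28 − 25 = 3 per arm. Nor do they give a reason to expect so strong a link between missing sessions in the first days of cycle 1 and neuropathy three months later, in patients with no baseline neuropathy.

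**Conclusion.** The contradiction between 9.2 and 11.0 is real, and so is the consequence of following 9.2: a post-randomisation exclusion that can act only in Arm A and that loses the primary 3-month score. Section 11.0 does not clearly prevent the loss, and section 16 does not repair it.

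The likely effect is small. With one of 28 removed and an assumed difference of 0.5-1.0 SD, the one-sided type I error is 5.7%-6.4% if the patient would have scored worse and 4.4%-3.8% if better; with no difference there is no bias.

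A reader might also infer that the plan favours acupuncture. The documents do not support that, because nothing in them indicates whether patients who miss these sessions would score worse or better. The point is a cheap improvement to a pilot, not a flaw that undermines it.

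**What to change.** - **Reconcile 9.2, 11.0 and 16.3** on removal from the study versus discontinuation of treatment, and on who may be replaced. Include the 11.0 sentence that patients with less than one cycle of chemotherapy are not followed, since it would otherwise block the next step.
- **Keep collecting data.** State that missing acupuncture sessions does not end data collection, and that the 12-week CIPN-20 is sought from every randomised patient where consent allows. It can be done by phone, on paper or electronically, as 10.2 already permits for the mid-cycle assessment. Do the Neuropen and tuning fork tests only where the patient is attending anyway, because they need trained staff in person. Sections 9.7 and 9.9 and the calendar should not contradict this.
- **Name the analysis set in 16.5:** all randomised patients with a 12-week score, by assigned arm, keeping any patient who was replaced.

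None of this changes who receives or stops acupuncture.

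The cost is wording, a few questionnaires and a slight dilution of the effect. If one of 28 Arm A patients gets no benefit, 0.7 SD becomes 0.7 × 27/28 = 0.675 SD. Like for like, power goes from about 78% (24 against 25 patients, 0.7 SD, patient lost) to about 76% (25 against 25, 0.675 SD, patient kept), about 2 points.
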